9.3.2 Covariates

The following information will be extracted from MDV in this study.

Table 2. Definition of variables

Variable	Data extraction period	Details
Sex	Index date	Male/Female
Age	Index date	Age at Index date
Comorbidity and medical history	12 months before the index date (included)	
 - Coronary heart disease - Gastro-esophageal reflux disease - Obstructive sleep apnoea syndrome - Chronic obstructive pulmonary disease (COPD) - Lung cancer - Pulmonary hypertension 
See Annex 4 for code to define each comorbidity and medical history

Underlying disease (Pre-specified ILD)	12 months before the index date (included)	
 - Underlying Autoimmune Disease (Autoimmune ILD, Non-autoimmune ILD, Multiple, Unknown) - ILD Category (Hypersensitive pneumonitis, Exposure-related ILD, idiopathic nonspecific interstitial pneumonia (iNSIP), Unclassifiable idiopathic interstitial pneumonias (IIP), Sarcoidosis, RA-ILD, SSc-ILD, mixed connective tissue disease-ILD (MCTD-ILD), Other autoimmune ILD, Other ILD, Multiple, Unknown) - Pre-Specified ILD Clinical Diagnosis (Hypersensitive pneumonitis, Exposure-related ILD, iNSIP, Unclassifiable IIP, Sarcoidosis, RA-ILD, SSc-ILD, MCTD-ILD, Systemic Lupus Erythematosus-ILD (SLE-ILD), Polymyositis/Dermatomyositis-ILD (PM/DM-ILD), Sjogren ILD, Other autoimmune ILD, Other ILD, Multiple, Unknown) 
See Annex 5 for algorithm to define underlying diseases

Treatment	6 months before the index date (included) Follow-up period	
 - Rituximab - Tacrolimus - Mycophenolate - Cyclosporine - Cyclophosphamide - Azathioprine - Oral Corticosteroid - Tocilizumab - Nintedanib 
See Annex 3 for code to define each treatment
 
As for corticosteroid and immunosuppressive drugs during follow-up period, the same condition used for criteria of progression to PF-ILD will be applied.

Management	Follow-up period	
 - Oxygen therapy (HOT) - Lung transplant - Palliative care (oxygen inhalation, opioid use) 
See Annex 3 for code to define each management

Clinical examination	6 months before the index date (included)	
 - Pulmonary function test - HRCT/CT - KL-6 - SP-D 
See Annex 3 for code to define each clinical examination

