9.7.3 Subgroup analysis

The three subgroup analyses by underlying diseases defined by disease codes on the index date and 12-months lookback period as described in Annex 5 will be performed for patient background characteristics and treatment, primary outcome, and secondary outcomes.

<Subgroup Patterns>

Underlying Autoimmune Disease (Subgroup1): Autoimmune ILD, Non-autoimmune ILD, Multiple, Unknown

ILD Category (Subgroup 2): Hypersensitive pneumonitis, Exposure-related ILD, iNSIP, Unclassifiable IIP, Sarcoidosis, RA-ILD, SSc-ILD, MCTD-ILD, Other autoimmune ILD, Other ILD, Multiple, Unknown

Pre-Specified ILD Clinical Diagnosis (Subgroup 3): Hypersensitive pneumonitis, Exposure-related ILD, iNSIP, Unclassifiable IIP, Sarcoidosis, RA-ILD, SSc-ILD, MCTD-ILD, SLE-ILD, PM/DM-ILD, Sjogren ILD, Other autoimmune ILD, Other ILD, Multiple, Unknown

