else if earliest underlying disease code=7109008 AND disease code on index date=in(J84.1, J84.9, 8840951, 8848245), **then** subgroup1=Autoimmune ILD, subgroup2=MCTD-ILD, subgroup3=MCTD-ILD

else if earliest underlying disease code=in(8841317, 8850417, 8848245, M35.2, M35.3, M35.4, M35.5, M35.6, M35.7, M35.8, M35.9, M30.0, M30.1, M30.2, M30.3, M30.8, M31.0, M31.1, M31.2, M31.3, M31.4, M31.6, M31.7, M31.8, M31.9) AND disease code on index date=in(J84.1, J84.9, 8840951, 8848245), **then** subgroup1= Autoimmune ILD, subgroup2=Other autoimmune ILD, subgroup3=Other autoimmune ILD

(2)Note: The earliest underlying disease codes in the same conditional statement are NOT considered different. For example, earliest underlying disease codes of D86.0 and D86.1 are in the same conditional statement and these are not considered different earliest underlying disease codes. On the other hand, earliest underlying disease codes of D86.0 and J67.0 are in the different conditional statement and these are considered different earliest underlying disease codes.

Step 3: Patients not grouped in the step 1 and 2 will be grouped based on the fibrosing-ILD code on the index date

else if disease code on index date=in(5163005, 5150011, 8849927) AND no other fibrosing-ILD code on the index date, **then** subgroup1=subgroup2=subgroup3=IPF. These patients will be excluded from study population.

else if two or more different ⁽³⁾ disease codes including disease code of IPF specified in this step 3 exist on index date, **then** subgroup1=subgorup2=subgrou3=Multiple

else if disease code on index date=in(8850547, 8845727), **then** subgroup1=Non-autoimmune ILD, subgroup2=iNSIP, subgroup3=iNSIP

else if disease code on index date=in(5168008, 5168009, 5150001, 8845731, 8845640, J84.9), **then** subgroup1=Non-autoimmune ILD, subgroup2=Unclassifiable IIP, subgroup3=Unclassifiable IIP

else if disease code on index date=in(1363003, 8845663, 8845714, 8845719, 5168010), **then** subgroup1=Non-autoimmune ILD, subgroup2=Other ILD, subgroup3=Other ILD

else if disease code on index date=in(8840951, 8848245), **then** subgroup1=Autoimmune ILD, subgroup2=Other autoimmune ILD, subgroup3=Other autoimmune ILD

else subgroup1=subgroup2=subgroup3=Unknown

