(3)Note: The disease codes in the same conditional statement are NOT considered different. For example, disease codes of 8850547 and 88457271 are in the same conditional statement and these are not considered different disease codes. On the other hand, disease codes of 8850547 and 5168008 are in the different conditional statement and these are considered different disease codes.

END

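### Annex 5 Step 3 lets the non-specific code J84.9 compete with specific Step 3 diagnoses, which moves patients out of the iNSIP and Other ILD subgroups

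*Combined protocol and SAP*

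**What the plan says.** Annex 5 sorts patients in three steps. The last is "Step 3: Patients not grouped in the step 1 and 2 will be grouped based on the fibrosing-ILD code on the index date". Its order is: IPF codes alone (excluded); Multiple; iNSIP (8850547, 8845727); Unclassifiable IIP; Other ILD (1363003, 8845663, 8845714, 8845719, 5168010); other autoimmune ILD (8840951, 8848245); Unknown.

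The Multiple line applies when two or more different "disease codes including disease code of IPF specified in this step 3 exist on index date". The Unclassifiable IIP branch reads "disease code on index date=in(5168008, 5168009, 5150001, 8845731, 8845640, J84.9", so J84.9 is one of its members. Note (3) explains what counts as different: "disease codes of 8850547 and 5168008 are in the different conditional statement and these are considered different disease codes". That example pairs an iNSIP code with an Unclassifiable IIP code and contains no IPF code.

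Annex 6 names two entries under J84.9: interstitial pneumonia (4860015) and interstitial lung disease (5168003). Both are labelled Non-autoimmune and Unclassifiable. Section 9.7.3 describes the subgroups as "defined by disease codes on the index date and 12-months lookback period", refers to Annex 5 for the detail, and repeats the primary outcome in each of them.

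**The concern.** J84.9 says that the patient has an interstitial lung disease but not which one. A hospital can record it beside a specific diagnosis without meaning a second disease. Step 3 has no rule for that case, so a patient with one disease coded at two levels of detail can be counted as having several, or can lose the specific label.

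Section 7 says the study will look at progression by underlying disease, and it names iNSIP and unclassifiable IIP separately. If membership of these groups depends on whether a non-specific code was entered on one particular day, the 6- to 24-month probabilities for iNSIP, Other ILD, Unclassifiable IIP and Multiple describe coding habits as well as disease. The wording of the Multiple line adds a second problem: two programmers could follow it and build different subgroups.

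**Working it through.** The plan states no figure on this point, so there is none to reproduce. The check applies the Step 3 chain as written to patients not placed in Steps 1 or 2, under both readings of the Multiple line.

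| Codes | Reading A: any two different codes | Reading B: an IPF code is required |
|---|---|---|
| iNSIP code alone on the index date | iNSIP | iNSIP |
| iNSIP code + J84.9 on the index date | Multiple | iNSIP (branch comes first) |
| Other ILD code (e.g. 8845714 or 8845719) + J84.9 on the index date | Multiple | Unclassifiable IIP (branch comes first) |
| J84.9 alone on the index date, iNSIP code earlier | Unclassifiable IIP | Unclassifiable IIP |
| J84.9 alone on the index date, Other ILD code earlier | Unclassifiable IIP | Unclassifiable IIP |
| IPF code + J84.9 on the index date | Multiple | Multiple |

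The example in Note (3) supports reading A. Under A, Multiple is assigned in all three subgroup patterns. An iNSIP + J84.9 patient therefore leaves Non-autoimmune ILD in Subgroup 1, although both codes are Non-autoimmune. The autoimmune codes 8840951 and 8848245, if Step 2 has not already placed the patient, behave like Other ILD codes, because their branch also follows the one holding J84.9.

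The documents do not say how often J84.9 accompanies or replaces a specific code. As an illustration for iNSIP, let *a* be the share with the iNSIP code on the index date, and *c* the share of those who also have J84.9 that day. Assume the remaining 1 − *a* have only J84.9 that day. Under reading A:

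- kept as iNSIP = *a*(1 − *c*)
- moved to Multiple = *a* × *c*
- moved to Unclassifiable IIP = 1 − *a*

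| *a* | *c* | Kept | Multiple | Unclassifiable IIP |
|---|---|---|---|---|
| 1.0 | 0 | 100% | 0% | 0% |
| 0.9 | 0.1 | 81% | 9% | 10% |
| 0.8 | 0.3 | 56% | 24% | 20% |
| 0.6 | 0.5 | 30% | 30% | 40% |

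Under reading B, iNSIP keeps the share *a*. An Other ILD group with the same assumed rates still keeps only *a*(1 − *c*), and the rest all go to Unclassifiable IIP: 9% + 10% = 19%, 24% + 20% = 44% and 30% + 40% = 70% in the last three rows. All values of *a* and *c* are assumptions.

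**The case against.** Several points on the other side stand.

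- The Multiple line can be read as requiring an IPF code, and Note (3) only defines what different means. The iNSIP + J84.9 route therefore depends on the reading. The Other ILD route and the earlier-code route do not.
- A reader might infer that Step 3 contradicts Table 2 and section 9.7.3, which mention the 12-month look-back. The documents do not support this: both refer to Annex 5, and the algorithm as a whole uses index-date codes and, in Step 2, the look-back.
- A reader might also infer that Step 2 follows the opposite principle. It does a different job: it links an ILD code to a separate underlying disease such as sarcoidosis or rheumatoid arthritis. It does not rank ILD codes by specificity.
- Sensitivity analysis 2 moves the index date to the first code. A patient whose first code date carries iNSIP alone is then labelled iNSIP. This covers only patients whose first code date carries the specific code. The new index day is again read alone, with no override of J84.9, and the start of follow-up moves as well.
- A later non-specific label may reflect a diagnosis that was reconsidered. Preferring an earlier specific code is a judgement, so it belongs in a sensitivity analysis and not in the main rule.

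None of this explains why J84.9 on the same day should displace a specific code.

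**Conclusion.** The concern holds for same-day coding and for the ambiguous Multiple line. Other ILD + J84.9 is misplaced on either reading, and iNSIP + J84.9 is misplaced on the reading that Note (3) supports. The earlier-code route also follows from the text on both readings, but the right label there is open to judgement.

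The reach is limited. The estimates affected are those for iNSIP, Other ILD (the Step 3 route only, since J84.0 patients enter through Step 2), Unclassifiable IIP and Multiple. Diseases assigned in Steps 1 and 2 are not displaced. A reader might infer that the primary result is wrong. It is not affected, because moving included patients between these groups leaves the overall Kaplan-Meier estimate unchanged. Nor do the documents support any particular size of loss: the 30% to 100% range above follows from assumed rates, and the direction of any bias in the subgroup probabilities is unknown.

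The change is worth making before the subgroup tables are produced.

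**What to change.** 1. In Step 3, let J84.9 assign Unclassifiable IIP only when no specific non-IPF Step 3 code (iNSIP, Other ILD, 8840951, 8848245) is present on the index date. J84.9 together with one such code should not create Multiple. The other codes in the Unclassifiable IIP branch stay as they are. Reword the Multiple line so that it has one reading, stating whether an IPF code is required.
2. Leave the IPF statement and the handling of an IPF code with another code unchanged. Extending the override to IPF codes would turn included patients into excluded ones and change the study population. Report how many included patients have an IPF code plus J84.9 on the index date.
3. Add a sensitivity subgroup analysis in which patients with only J84.9 on the index date take a specific non-IPF Step 3 code found in the 12-month look-back. The eligibility criteria set no maximum gap between the two qualifying codes, so this will miss some earlier codes; say so in the report.

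The cost is a wording change in Annex 5, a few program lines and one extra set of subgroup tables. No new data are needed. The drawback of item 3 is that an earlier specific code may since have been revised, which is why it is not the main rule.

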ANNEX 6. INFORMATION OF THE CODE TO DEFINE FIBROSING ILD AND UNDERLYING DISEASES

Disease	ICD-10 Code	billing code	Underlying Autoimmune Disease	ILD Category	Pre-Specified ILD Clinical Diagnosis
respiratory disorder in dermatosclerosis	M348	8844510	autoimmune	SSc-ILD	SSc-ILD
rheumatoid arthritis interstitial pneumonia	M0510	8847737	autoimmune	RA-ILD	RA-ILD
respiratory disorder complicated by granulomatosis with polyangiitis	M313	8848382	autoimmune	Other autoimmune ILDs	Other autoimmune ILDs
systemic lupus erythematosus interstitial pneumonia	M321	8848278	autoimmune	SLE-ILD	other autoimmune ILDs
respiratory disorder in systemic lupus erythematosus	M321	8836513	autoimmune	SLE-ILD	other autoimmune ILDs
interstitial pneumonia in juvenile dermatomyositis	M330	8848267	autoimmune	PM/DM ILD	other autoimmune ILDs
interstitial pneumonia in dermatomyositis	M331	8848302	autoimmune	PM/DM ILD	other autoimmune ILDs
respiratory disorder in dermatomyositis	M331	8839362	autoimmune	PM/DM ILD	other autoimmune ILDs
interstitial pneumonia in polymyositis	M332	8848283	autoimmune	PM/DM ILD	other autoimmune ILDs
respiratory disorder in polymyositis	M332	8837013	autoimmune	PM/DM ILD	other autoimmune ILDs
respiratory disorder in Sjogren's syndrome	M350	8834158	autoimmune	Sjogren ILD	other autoimmune ILDs

Disease	ICD-10 Code	billing code	Underlying Disease	Autoimmune	ILD Category	Pre-Specified Diagnosis	ILD	Clinical
postinflammatory pulmonary fibrosis	J841	8845640	Non-autoimmune		Unclassifiable	Unclassifiable		
usual interstitial pneumonia	J841	5168008	Non-autoimmune		Unclassifiable	Unclassifiable		
idiopathic interstitial pneumonia	J841	5168009	Non-autoimmune		Unclassifiable	Unclassifiable		
diffuse interstitial pneumonia	J841	5150001	Non-autoimmune		Unclassifiable	Unclassifiable		
diffuse alveolar damage	J841	8845731	Non-autoimmune		Unclassifiable	Unclassifiable		
idiopathic pulmonary fibrosis	J841	5163005	IPF		IPF	IPF		
pulmonary fibrosis	J841	5150011	IPF		IPF	IPF		
combined pulmonary fibrosis and emphysema	J841	8849927	IPF		IPF	IPF		
Idiopathic nonspecific interstitial pneumonia	J841	8850547	Non-autoimmune		iNSIP	iNSIP		

nonspecific interstitial pneumonia	J841	8845727	Non-autoimmune	iNSIP	iNSIP
acute interstitial pneumonia	J84.1	1363003	Non-autoimmune	Other IIPs	Other IIPs
respiratory bronchiolitis-associated interstitial lung disease	J841	8845663	Non-autoimmune	Other IIPs	Other IIPs
cryptogenic organizing pneumonia	J841	8845714	Non-autoimmune	Other IIPs	Other IIPs
desquamative interstitial pneumonia	J841	8845719	Non-autoimmune	Other IIPs	Other IIPs
lymphocytic interstitial pneumonia	J841	5168010	Non-autoimmune	Other IIPs	Other IIPs
-	-	-	Non-autoimmune	Unclassifiable	Unclassifiable
interstitial pneumonia	J849	4860015	Non-autoimmune	Unclassifiable	Unclassifiable
interstitial lung disease	J849	5168003	Non-autoimmune	Unclassifiable	Unclassifiable
respiratory disorder in dermatosclerosis	M348	8844510		SSc-ILD	SSc-ILD
respiratory disorder complicated by granulomatosis with polyangiitis	M313	8848382		other CTD-ILD	other CTD-ILD
lupus pneumonia	M321	8844341		SLE-ILD	SLE-ILD

systemic lupus erythematosus interstitial pneumonia	M321	8848278		SLE-ILD	SLE-ILD
respiratory disorder in systemic lupus erythematosus	M321	8836513		SLE-ILD	SLE-ILD
interstitial pneumonia in juvenile dermatomyositis	M330	8848267		PM/DM-ILD	PM/DM-ILD
interstitial pneumonia in dermatomyositis	M331	8848302		PM/DM-ILD	PM/DM-ILD
respiratory disorder in dermatomyositis	M331	8839362		PM/DM-ILD	PM/DM-ILD
interstitial pneumonia in polymyositis	M332	8848283		PM/DM-ILD	PM/DM-ILD
respiratory disorder in polymyositis	M332	8837013		PM/DM-ILD	PM/DM-ILD
respiratory disorder in Sjogren's syndrome	M350	8834158		Sjogren-ILD	Sjogren-ILD
interstitial pneumonia due to collagen disease	M351	8848245		other CTD-ILD	other CTD-ILD
rheumatoid lung disease	M0510	8840951		other CTD-ILD	
rheumatoid arthritis interstitial pneumonia	M0510	8847737		RA-ILD	RA-ILD

N-Total number of study patients in each ILD underlying autoimmune disease category, IPF – Idiopathic Pulmonary Fibrosis, iNSIP – Idiopathic Nonspecific Interstitial Pneumonia, IIP – Idiopathic Interstitial Pneumonia, SSc-ILD – Systemic Sclerosis- Associated ILD, RA-ILD – Rheumatoid-Associated ILD, SLE-ILD – Systemic Lupus Erythematosus ILD, PM/DM ILD – Polymyositis/Dermatomyositis ILD

Disease	ICD-10 Code	billing code	Linkage Fibrotic code	Underlying Autoimmune Disease	ILD Category	Pre-Specified ILD Clinical Diagnosis
Sjogren's syndrome	M350	7102001	J84.1, J84.8, J84.9, J99.0, J99.1	Autoimmune	Other-autoimmune/CTD ILD	Sjogren ILD
Sjogren's syndrome myopathy	M350	8841440	J84.1, J84.8, J84.9, J99.0, J99.1	Autoimmune	Other-autoimmune/CTD ILD	Sjogren ILD
respiratory disorder in Sjogren's syndrome	M350	8834158	J84.1, J84.8, J84.9, J99.0, J99.1	Autoimmune	Other-autoimmune/CTD ILD	Sjogren ILD
primary Sjogren's syndrome	M350	8848230	J84.1, J84.8, J84.9, J99.0, J99.1	Autoimmune	Other-autoimmune/CTD ILD	Sjogren ILD
secondary Sjogren's syndrome	M350	8848298	J84.1, J84.8, J84.9, J99.0, J99.1	Autoimmune	Other-autoimmune/CTD ILD	Sjogren ILD

overlap syndrome	M351	8841317	J84.1, J84.8, J84.9, J99.0, J99.1	Autoimmune	Other-autoimmune/CTD ILD	Other-autoimmune/CTD ILD
anti-ARS antibody syndrome	M351	8850417	J84.1, J84.8, J84.9, J99.0, J99.1	Autoimmune	Other-autoimmune/CTD ILD	Other-autoimmune/CTD ILD
mixed connective tissue disease	M351	7109008	J84.1, J84.8, J84.9, J99.0, J99.1	Autoimmune	MCTD-ILD	MCTD-ILD
interstitial pneumonia due to collagen disease	M351	8848245	J84.1, J84.8, J84.9, J99.0, J99.1	Autoimmune	Other-autoimmune/CTD ILD	Other-autoimmune/CTD ILD
Behcet's disease	M352	1361002	J84.1, J84.8, J84.9, J99.0, J99.1	Autoimmune	Other-autoimmune/CTD ILD	Other-autoimmune/CTD ILD
vulval Behcet's disease	M352	1361011	J84.1, J84.8, J84.9, J99.0, J99.1	Autoimmune	Other-autoimmune/CTD ILD	Other-autoimmune/CTD ILD

ocular Behcet's disease	M352	8845881	J84.1, J84.8, J84.9, J99.0, J99.1	Autoimmune	Other-autoimmune/CTD ILD	Other-autoimmune/CTD ILD
vasculo-Behcet's disease	M352	1361009	J84.1, J84.8, J84.9, J99.0, J99.1	Autoimmune	Other-autoimmune/CTD ILD	Other-autoimmune/CTD ILD
oral Behcet's disease	M352	1361010	J84.1, J84.8, J84.9, J99.0, J99.1	Autoimmune	Other-autoimmune/CTD ILD	Other-autoimmune/CTD ILD
neuro-Behcet disease	M352	1361005	J84.1, J84.8, J84.9, J99.0, J99.1	Autoimmune	Other-autoimmune/CTD ILD	Other-autoimmune/CTD ILD
entero-Behcet disease	M352	8842203	J84.1, J84.8, J84.9, J99.0, J99.1	Autoimmune	Other-autoimmune/CTD ILD	Other-autoimmune/CTD ILD
incomplete Behcet disease	M352	8846052	J84.1, J84.8, J84.9, J99.0, J99.1	Autoimmune	Other-autoimmune/CTD ILD	Other-autoimmune/CTD ILD
polymyalgia rheumatica	M353	7250004	J84.1, J84.8, J84.9, J99.0, J99.1	Autoimmune	Other-autoimmune/CTD ILD	Other-autoimmune/CTD ILD

diffuse eosinophilic fasciitis	M354	8839540	J84.1, J84.8, J84.9, J99.0, J99.1	Autoimmune	Other-autoimmune/CTD ILD	Other-autoimmune/CTD ILD
eosinophilic fasciitis	M354	7294009	J84.1, J84.8, J84.9, J99.0, J99.1	Autoimmune	Other-autoimmune/CTD ILD	Other-autoimmune/CTD ILD
acrosclerosis	M355	7108005	J84.1, J84.8, J84.9, J99.0, J99.1	Autoimmune	Other-autoimmune/CTD ILD	Other-autoimmune/CTD ILD
multifocal fibrosclerosis	M355	8836987	J84.1, J84.8, J84.9, J99.0, J99.1	Autoimmune	Other-autoimmune/CTD ILD	Other-autoimmune/CTD ILD
Weber-Christian disease	M356	8830767	J84.1, J84.8, J84.9, J99.0, J99.1	Autoimmune	Other-autoimmune/CTD ILD	Other-autoimmune/CTD ILD
hyperkinetic syndrome	M357	7285007	J84.1, J84.8, J84.9, J99.0, J99.1	Autoimmune	Other-autoimmune/CTD ILD	Other-autoimmune/CTD ILD

familial ligament relaxation	M357	8831279	J84.1, J84.8, J84.9, J99.0, J99.1	Autoimmune	Other-autoimmune/CTD ILD	Other-autoimmune/CTD ILD
eosinophilia-myalgia syndrome	M358	7101038	J84.1, J84.8, J84.9, J99.0, J99.1	Autoimmune	Other-autoimmune/CTD ILD	Other-autoimmune/CTD ILD
IgG4-related disease	M359	8848113	J84.1, J84.8, J84.9, J99.0, J99.1	Autoimmune	Other-autoimmune/CTD ILD	Other-autoimmune/CTD ILD
systemic autoimmune disease	M359	8836526	J84.1, J84.8, J84.9, J99.0, J99.1	Autoimmune	Other-autoimmune/CTD ILD	Other-autoimmune/CTD ILD
collagen disease	M359	7109004	J84.1, J84.8, J84.9, J99.0, J99.1	Autoimmune	Other-autoimmune/CTD ILD	Other-autoimmune/CTD ILD
anemia associated with collagen disease	M359	8833428	J84.1, J84.8, J84.9, J99.0, J99.1	Autoimmune	Other-autoimmune/CTD ILD	Other-autoimmune/CTD ILD
pericarditis of collagen disease	M359	4239017	J84.1, J84.8, J84.9, J99.0, J99.1	Autoimmune	Other-autoimmune/CTD ILD	Other-autoimmune/CTD ILD
polyarteritis nodosa	M300	8833125	J84.1, J84.8, J84.9, J99.0, J99.1	Autoimmune	Other-autoimmune/CTD ILD	Other-autoimmune/CTD ILD

eosinophilic granulomatosis with polyangiitis	M301	8848338	J84.1, J84.8, J84.9, J99.0, J99.1	Autoimmune	Other-autoimmune/CTD ILD	Other-autoimmune/CTD ILD
juvenile multiple arteritis	M302	8835258	J84.1, J84.8, J84.9, J99.0, J99.1	Autoimmune	Other-autoimmune/CTD ILD	Other-autoimmune/CTD ILD
acute febrile mucocutaneous lymph node syndrome	M303	4461009	J84.1, J84.8, J84.9, J99.0, J99.1	Autoimmune	Other-autoimmune/CTD ILD	Other-autoimmune/CTD ILD
Kawasaki's disease	M303	4461003	J84.1, J84.8, J84.9, J99.0, J99.1	Autoimmune	Other-autoimmune/CTD ILD	Other-autoimmune/CTD ILD
ischemic heart disease due to Kawasaki's disease	M303	8831474	J84.1, J84.8, J84.9, J99.0, J99.1	Autoimmune	Other-autoimmune/CTD ILD	Other-autoimmune/CTD ILD
Kawasaki disease-related coronary artery aneurysm	M303	4461004	J84.1, J84.8, J84.9, J99.0, J99.1	Autoimmune	Other-autoimmune/CTD ILD	Other-autoimmune/CTD ILD
incomplete Kawasaki disease	M303	8846336	J84.1, J84.8, J84.9, J99.0, J99.1	Autoimmune	Other-autoimmune/CTD ILD	Other-autoimmune/CTD ILD
polyangiitis overlap syndrome	M308	8837016	J84.1, J84.8, J84.9, J99.0, J99.1	Autoimmune	Other-autoimmune/CTD ILD	Other-autoimmune/CTD ILD

skin polyarteritis nodosa	M308	8846209	J84.1, J84.8, J84.9, J99.0, J99.1	Autoimmune	Other-autoimmune/CTD ILD	Other-autoimmune/CTD ILD
cutaneous arteritis	M308	8849445	J84.1, J84.8, J84.9, J99.0, J99.1	Autoimmune	Other-autoimmune/CTD ILD	Other-autoimmune/CTD ILD
Goodpasture's syndrome	M310	4462001	J84.1, J84.8, J84.9, J99.0, J99.1	Autoimmune	Other-autoimmune/CTD ILD	Other-autoimmune/CTD ILD
hypersensitivity vasculitis	M310	4462002	J84.1, J84.8, J84.9, J99.0, J99.1	Autoimmune	Other-autoimmune/CTD ILD	Other-autoimmune/CTD ILD
cutaneous leukocytoclastic vasculitis	M310	8851019	J84.1, J84.8, J84.9, J99.0, J99.1	Autoimmune	Other-autoimmune/CTD ILD	Other-autoimmune/CTD ILD
drug-induced hypersensitivity vasculitis	M310	8844108	J84.1, J84.8, J84.9, J99.0, J99.1	Autoimmune	Other-autoimmune/CTD ILD	Other-autoimmune/CTD ILD
thrombotic thrombocytopenic purpura	M311	4466002	J84.1, J84.8, J84.9, J99.0, J99.1	Autoimmune	Other-autoimmune/CTD ILD	Other-autoimmune/CTD ILD
thrombotic microangiopathy	M311	8833136	J84.1, J84.8, J84.9, J99.0, J99.1	Autoimmune	Other-autoimmune/CTD ILD	Other-autoimmune/CTD ILD
acquired thrombotic thrombocytopenic purpura	M311	8849965	J84.1, J84.8, J84.9, J99.0, J99.1	Autoimmune	Other-autoimmune/CTD ILD	Other-autoimmune/CTD ILD
congenital thrombotic thrombocytopenic purpura	M311	8847881	J84.1, J84.8, J84.9, J99.0, J99.1	Autoimmune	Other-autoimmune/CTD ILD	Other-autoimmune/CTD ILD
gangrenous rhinitis	M312	4609006	J84.1, J84.8, J84.9, J99.0, J99.1	Autoimmune	Other-autoimmune/CTD ILD	Other-autoimmune/CTD ILD

localized granulomatosis with polyangiitis	M313	8848336	J84.1, J84.8, J84.9, J99.0, J99.1	Autoimmune	Other-autoimmune/CTD ILD	Other-autoimmune/CTD ILD
generalized granulomatosis with polyangiitis	M313	8848371	J84.1, J84.8, J84.9, J99.0, J99.1	Autoimmune	Other-autoimmune/CTD ILD	Other-autoimmune/CTD ILD
granulomatosis with polyangiitis	M313	8848381	J84.1, J84.8, J84.9, J99.0, J99.1	Autoimmune	Other-autoimmune/CTD ILD	Other-autoimmune/CTD ILD
respiratory disorder complicated by granulomatosis with polyangiitis	M313	8848382	J84.1, J84.8, J84.9, J99.0, J99.1	Autoimmune	Other-autoimmune/CTD ILD	Other-autoimmune/CTD ILD
Takayasu's arteritis	M314	8848380	J84.1, J84.8, J84.9, J99.0, J99.1	Autoimmune	Other-autoimmune/CTD ILD	Other-autoimmune/CTD ILD
aortitis syndrome	M314	4467003	J84.1, J84.8, J84.9, J99.0, J99.1	Autoimmune	Other-autoimmune/CTD ILD	Other-autoimmune/CTD ILD
-	-	-	-	Autoimmune	Other-autoimmune/CTD ILD	Other-autoimmune/CTD ILD
giant cell arteritis	M316	4465001	J84.1, J84.8, J84.9, J99.0, J99.1	Autoimmune	Other-autoimmune/CTD ILD	Other-autoimmune/CTD ILD

microscopic polyangiitis	M317	8842086	J84.1, J84.8, J84.9, J99.0, J99.1	Autoimmune	Other-autoimmune/CTD ILD	Other-autoimmune/CTD ILD
ANCA-associated vasculitis	M318	8845513	J84.1, J84.8, J84.9, J99.0, J99.1	Autoimmune	Other-autoimmune/CTD ILD	Other-autoimmune/CTD ILD
hypocomplementemic urticarial vasculitis	M318	8849413	J84.1, J84.8, J84.9, J99.0, J99.1	Autoimmune	Other-autoimmune/CTD ILD	Other-autoimmune/CTD ILD
necrotizing angitis	M319	4460015	J84.1, J84.8, J84.9, J99.0, J99.1	Autoimmune	Other-autoimmune/CTD ILD	Other-autoimmune/CTD ILD
polyangiitis	M319	4460017	J84.1, J84.8, J84.9, J99.0, J99.1	Autoimmune	Other-autoimmune/CTD ILD	Other-autoimmune/CTD ILD

N-Total number of study patients in each ILD underlying autoimmune disease category,

SSc-ILD – Systemic Sclerosis- Associated ILD, RA-ILD – Rheumatoid-Associated ILD, SLE-ILD – Systemic Lupus Erythematosus ILD, PM/DM ILD – Polymyositis/Dermatomyositis ILD

CTD-ILD – connective tissue disease- associated ILD, MCTD-ILD – Mixed Connective Tissue Disease-ILD

